14. STATISTICAL CONSIDERATIONS

14.1 Data Analysis and Statistical Modeling Plan

Specific Aim 1. Qualitative data will document how the investigators support the participating organizations to implement and sustain the intervention. As a broad implementation aim, there are no hypotheses associated with this aim. Instead, the focus will be on describing the process of assisting the organizations with implementation and maintenance. This description and summary will be generated from interviews and notes from project calls, along with other qualitative data that is gathered throughout the study.

Specific Aim 2. To evaluate the use and effectiveness of implementation strategies over time, and identify barriers and facilitators to organizational adoption of guidelines, provider adherence to guidelines, feasibility, and sustainability, the investigators will draw on the Consolidated Framework for Implementation Research (CFIR),¹⁸ which provides an analytic rubric for examining intervention and provider characteristics, as well as inner and outer settings. Data regarding acceptability, barriers, and facilitators will be derived from interviews and implementation-focused evaluation measures. As the investigators are examining implementation in two large healthcare organizations, barriers and facilitators will likely vary by agency. Descriptive statistics will be used to analyze the survey data, given the small sample size and the modest, practical goal of characterizing the agencies in preparation for implementation. In addition, the investigators will examine the facilitator/navigator and participant satisfaction ratings to characterize acceptability of the intervention. These ratings will be compared both within and across cohorts and organizations. Potential determinants of adoption and fidelity include but are not limited to training factors, competency at delivering the intervention, types of facilitators/navigators, participant “mix” (including gender and racial/ethnic diversity) in a given cohort, retention, and satisfaction. All of these factors will be examined when characterizing fidelity across agencies. In addition, based on interviews with facilitators/navigators and clients, the investigators will remain open to other determinants that may emerge during implementation. There are several possible determinants of maintenance. The investigators hypothesize that sustainability will be achieved in agencies that have their own trained staff facilitators who deliver the intervention with fidelity and who had positive experiences with the intervention during the implementation phase.

Qualitative data analysis: All interviews will be digitally recorded and transcribed by a professional transcription company. Analysis will be conducted primarily by [name] and [name] (who has been trained by [name]), utilizing ATLAS.ti, a software package that allows for fluid “interaction” of data types and sources. Using constant comparison analytic methods,¹¹⁰ a preliminary codebook will be developed both deductively using CFIR and inductively from a sub-sample of interviews within and across organizations at baseline. Qualitative findings at baseline will be augmented by preliminary analyses of staff-level data from the structured measures described above (e.g., burnout, organizational climate, etc.), and a baseline profile will be developed for each agency. These profiles will be reviewed by the Implementation Team, and will be used to tailor implementation strategies at each site (e.g., where there is a high level of burnout, additional attention will be paid to supporting staff and managing workload throughout implementation). This approach of using baseline data as diagnostic and informative for tailored implementation has been employed by [name] in a prior implementation study.¹¹¹ The codebook will be elaborated upon and adjusted as each round of interviews is reviewed until thematic saturation is achieved within and across cycles of interviews. Interviews will be compared within each organization, across organizations, across different types of respondents, and over time. Additional sources of qualitative data (i.e. meeting minutes, monthly reflections, archival information) will also be included in the data set. The investigators will analyze the data specifically for barriers to and facilitators of implementation, including but not limited to the ways in which the project’s implementation strategies affect adoption, fidelity, and sustainability. In addition to identifying themes and patterns qualitatively, the investigators will examine statistical associations between important process and outcome variables such as satisfaction with the intervention, fidelity, and retention, and improvement in behavioral outcomes. Agency profiles will be revisited and further developed at the end of the active implementation phase, and again after implementation, thereby creating a story of implementation at each organization.

Specific Aim 3. To evaluate the clinical outcomes (e.g., improvement on a CVD risk factor or on the 5- or 7-item score) and the effects of the intervention, systematic data analysis and statistical modeling will be carried out: (1) For univariate analysis, the marginal distribution of each measure obtained will be calculated at each time point and across time. For categorical variables (e.g., gender, and race/ethnicity), the frequency distribution and modes will be calculated. For continuous measures (e.g., blood sugar levels/HbA1c), the investigators will calculate the central location (mean and median), variation (standard deviation, kurtosis, etc.), percentiles and range. Statistical tests (e.g., Shapiro-Wilk test) will be used to assess normality of the outcomes. The investigators will evaluate the degree and patterns of missingness, and perform imputation (e.g., multiple imputation), if needed. (2) Bivariate analyses of each outcome measure and independent variables will be carried out. Pearson and Spearman rank correlation will be used to correlate predictors with outcome measures. T-test, analysis of variance (ANOVA) or marginal regressions will be used for continuous measures. The change (delta) of outcome measures between timepoints will be calculated, and distributions of the deltas will be carefully examined. The bivariate analyses between the deltas and covariates will be carried out. Marginal repeated measures models (see model structure below in (3)) will be carried out between each independent measure and outcomes over time. (3) Multivariate repeated measures modeling^{112,113}: To evaluate the relationships between outcome measures and independent variables over time, generalized linear mixed effect models (GLMEM) will be fitted $Y_i = X_i\alpha + Z_i\gamma_i + \varepsilon_i$, controlling for age and others factors. Graphical analyses (e.g., parallel plots) will be used to assist in examining the relationship between predictors and outcome measures over time. Potential non-linear relationships between the outcome measures and the continuous predictors will be explored through generalized additive mixed models.

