5.2 Inclusion and Exclusion Criteria

Agency sample

All 21 staff across the two agencies will be asked to complete the organizational-level measures described below. A subset of these individuals who are directly involved in implementation will be asked to participate in semi-structured interviews during the pre-conditions, implementation, and maintenance phases.

Client sample

The client participants will consist of 260 African American and Latino men and women who will be recruited from OASIS and NEVHC (~130 per agency), where they have received care on at least one occasion for testing or treatment. We will advertise at the agencies with flyers and brochures, developed in collaboration with agency leadership and staff. Patients will be eligible to participate if they are: 1) between 18 and 60 years of age; 2) HIV-positive; 3) are confident that they will remain in the city for at least five months; 4) have no plans to relocate beyond a reasonable distance from the study site; 5) agree to allow HHMB staff to view their medical records for test results having to do with CVD risks (e.g., high cholesterol, weight gain, a history of diabetes or high blood pressure, etc.); and 6) are willing to participate, speaking in English or Spanish. To be eligible, clients must also have greater than 0 on the LADS⁶¹ (see Screening and Enrollment, below), and must identify at least one CVD risk factor on the worksheet.

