Within the clinical and behavioral domain, the intervention targets the development of an action plan for health, promotes the strengthening of ties to individuals and the community, and empowers the participant toward greater resilience and post-traumatic growth. These skills and practices are intended to build towards the goal of breaking down the barriers that traumatic experiences pose to seeking and enacting better health practices, namely, CVD risk reduction (smoking cessation, exercise, stress reduction, etc.). Additionally, to this end, the intervention will also draw upon relevant concepts in the evidence-based *Diabetes Prevention Program*,⁹⁵ including the use of health navigators or coaches who help participants navigate through decisions and systems to CV risk reduction services. Health navigators or coaches have been documented to improve and sustain health habits.⁹⁶ In the *Action Plan for Health* component of the intervention, participants will incorporate CVD risk reduction using a CVD scorecard based on the American Heart Association Life's Simple Seven/My Healthy Heart program.⁸³ The scorecard identifies seven biologic and behavioral risk factors for CVD and whether the participant is at goal, in the caution range, or not at goal for each risk factor. Five of the seven risk factors (blood pressure control, healthy weight, healthy diet, physical activity, and smoking) are either self-reported or measured as part of the study. Two risk factors (cholesterol and blood sugar control) will be obtained from the electronic health record (available at both agencies). The investigators will also construct two

composite scores: a 5-item score without blood sugar or lipid levels and a 7-item score consisting of all the items. The 5-item score will be used for those who have not had LDL cholesterol or glucose control measured during the relevant study period. The facilitator/navigator will help each participant develop an action plan and goal card for one risk factor that is not at goal. The action plan will be reviewed and modified as needed during the HHMB program. At follow-up visits, participants will be encouraged to review their goal cards with their primary care provider at routine visits, and the navigator will work with the study participant to reassess his or her understanding of CVD risk and whether there is improvement in the risk factor selected.

Organizational-Level Implementation Strategies

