7. RECRUITMENT AND SCREENING PROCEDURES

Staff Recruitment: Staff will be recruited by one of the study PIs, [name], by email. This email will ask providers and staff to complete a brief survey, and key stakeholders will also be asked to participate in a qualitative interview. The measures will be completed via an online survey, and [name] will coordinate the consent process and the completion of measures. Secure, password-protected links will be used to ensure confidentiality of all data. Baseline organizational data will be used to inform subsequent phases, particularly tailoring of strategies at each agency.

Client Recruitment and Screening: In response to study flyers and brochures, clients will make phone or in-person contact with project staff to express their interest in participating. Potential participants will then be screened to determine their eligibility (see Client sample, above) using two measures: (1) the 6-item *UCLA Life Adversities Screener (LADS)*, a validated brief assessment of trauma and adversity history that has demonstrated a strong relationship to post-traumatic stress symptoms, depression, and anxiety ([name] et al., 2015).⁶¹ The six items include: childhood and adult sexual abuse; family adversity; family/community violence; discrimination; intimate partner violence; and lack of basic needs; and (2) the *Cardiovascular Patient Worksheet*, a one-page self-report form (developed for a VA-based CVD risk reduction implementation study) that asks clients about CVD-related illnesses, pregnancy complications, and family history, as well as smoking and exercise behaviors. To be eligible for HHMB, clients must have greater than 0 on the LADS, and must identify at least one CVD risk factor on the worksheet. Those who are eligible and interested in participating will be consented and then scheduled for the baseline assessment (see below). Sociodemographic information on individuals who do not meet eligibility criteria or refuse to participate and reasons for non-eligibility or refusal will be collected to permit comparisons between eligible participants and non-participants.

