2016). *Post-traumatic growth* will be assessed through analysis of participants' trauma writing⁹⁴ using the *Linguistic Inquiry and Word Count* program (LIWC), which counts certain linguistic classes of words associated with various outcomes of interest. For example, insight words such as "realize" and "see" are associated with reduced psychological distress and improvement in health status.¹⁰³ The investigators will calculate insight words as well as words associated with health and mental health (e.g. distress words, health habits).

| Summary of Baseline and Outcome Measures | |
|--|--|
| Intervention Targets of Change | Measures |
| Cognitive | BDI-II, PDS, LIWC |
| Affective | DERS, BDI-II, PDS, PHQ-15, LIWC |
| Clinical | CVD risk factors and goal(s), 5-item and 7-item scores |
| Behavioral | LIWC, PSQI, ISI |

Cardiovascular Health: Given the strong association between sleep and CVD risk,¹⁰⁴ the investigators

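### Aim 3 does not fix its clinical outcome: the score's items depend on laboratory availability, the action-plan factor is one reading, and the single-group change is worded as an effect

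*Combined protocol and SAP*

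**What the plan says.** Section 14.1 (Specific Aim 3) introduces the clinical outcome by example: "improvement on a CVD risk factor or on the 5- or 7-item score". The measures table in sections 8/9 lists, unranked, "CVD risk factors and goal(s), 5-item and 7-item scores". Section 12.1 refers back to sections 8 and 9 and adds its own open list, which names neither score. Sections 8/9 have three assessments (before, after and at 3 months), and no primary one is named.

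Section 6 describes the scorecard, which records "whether the participant is at goal, in the caution range, or not at goal for each risk factor". No points are assigned to these levels. On the action plan it says: "The facilitator/navigator will help each participant develop an action plan and goal card for one risk factor that is not at goal". At follow-up the navigator reassesses "whether there is improvement in the risk factor selected". On the composites it says: "The 5-item score will be used for those who have not had LDL cholesterol or glucose control measured during the relevant study period". By implication everyone else gets the 7-item score. The two laboratory items come from the electronic health record, and the period is not defined.

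Sections 1 and 2 word Aim 3 as evaluating the effect of HHMB on outcomes, and 14.1 also speaks of effects of the intervention. Section 4 states a within-subject pre/post design. Section 6 has provider education, audit and feedback, and notification of providers about clients needing CVD care running during implementation.

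**The concern.** Each permitted reading of the outcome behaves differently when nothing has changed.

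- A factor picked because it is in a poor state has more room to improve than to worsen.
- A score whose item set follows record availability is not the same quantity in every person. If the period is read per visit, it is not the same quantity within a person either.
- A five-item score computed identically for everyone has neither problem.

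The choice can be made after the data are seen, so the same data could be reported as a clinical gain or as no change. Whichever is chosen, a single-group change reported as an effect of HHMB claims more than the design can isolate. For the CVD outcomes the provider strategies are a further, planned cause of change.

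**Working it through.** The plan states no figure to reproduce here: 260 participants are given without alpha, power, effect size or SD. The numbers below are illustrations. The three levels and the 5 and 7 items come from section 6. The level shares, retest correlations and point values are assumptions.

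**1. Is the outcome fixed anywhere?** Section 14.1 offers alternatives joined by *or*. The table in 8/9 lists them side by side. Section 12.1 points back to 8/9 and gives examples without either score. No section defines improvement, ranks the candidates or names a visit. The choice stays open.

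**2. Action-plan factor, no true change.** Assume the following:
- a latent normal value with the same distribution at both visits;
- retest correlation r;
- a share w in the worst level;
- only the worst level eligible for selection;
- the value used for selection is also the baseline value.

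With k = Φ⁻¹(1 − w):

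P(better | worst) = 1 − Φ₂(−k, −k; r) / w

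Example: w = 0.30, k = 0.524, r = 0.7 gives Φ₂ = 0.1905, and 1 − 0.1905/0.30 = 0.365.

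| Share not at goal | r = 0.7 | r = 0.8 | r = 0.9 |
|---|---|---|---|
| 30% | 36.5% | 29.6% | 20.8% |
| 40% | 30.6% | 24.8% | 17.4% |
| 50% | 25.3% | 20.5% | 14.4% |

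So 14-37% improve a level. None can worsen, because there is no lower level. If the caution range also counts as eligible (at goal/caution/not at goal 40/30/30, 30/30/40 or 25/25/50), 16-34% improve and 9-14% worsen. The imbalance is smaller but points the same way.

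**3. Changing item set, raw sums.** Score the levels 2 (at goal), 1 (caution) and 0 (not at goal). The mean item score is μ = 2 × share at goal + share in caution. A person who goes from 5 to 7 items gains 2μ on average with no change in health:
- 40/30/30: μ = 0.80 + 0.30 = 1.10, gain 2.2
- 30/30/40: μ = 0.60 + 0.30 = 0.90, gain 1.8
- 25/25/50: μ = 0.50 + 0.25 = 0.75, gain 1.5

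If a net 10% of participants gained two items, the group mean would rise by 0.10 × 1.5 to 0.10 × 2.2, or 0.15-0.22 points. A net flow the other way lowers it equally. With percent-of-maximum scoring, the expected score is μ/2 (55%, 45% or 37.5%) on either item set, so the mean bias vanishes if the laboratory items are distributed like the others. Even with a fixed set per person, raw ranges differ between people: 0-10 on five items and 0-14 on seven.

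**4. Attribution.** Section 4 has no comparator. Section 6 has provider education, feedback and notification in the same clinics and period. A change in blood pressure or smoking could come from the sessions, from the provider strategies or from time. The design does not separate them.

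**5. Entry rule.** Sections 5.2 and 7 require that clients "must identify at least one CVD risk factor on the worksheet". Section 7 places this worksheet before the baseline assessment and has it cover CVD-related illness, "pregnancy complications, and family history, as well as smoking and exercise behaviors". Selection is therefore on a different form at a different occasion. If screening, baseline and follow-up are equally correlated with one another, the expected baseline and follow-up values given the screening answer are equal, and the expected chance change is about zero. If correlation decays with time, some regression to the mean remains. The documents do not allow its size to be estimated.

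**The case against.** A single-group pre/post comparison is openly declared and is a legitimate choice in a hybrid study. Section 14.1 plans deltas and mixed models, which count worsening as well as improvement when run on a fixed score. Both composites are to be constructed, the 5-item score could be computed for everyone, and imputation is foreseen. All of this stands, and it is why the remedy needs only wording. It does not remove the section 6 rule that assigns the score by laboratory availability.

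Three stronger readings are tempting, and the documents support none of them.

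- A reader might infer that the action-plan factor is the planned outcome, and that a false gain is nearly certain. The reassessment sentence stands in the intervention section and describes coaching. Section 14.1 says only a CVD risk factor, does not link it to the action plan and names no test of that factor against zero. The reading is possible, not stated.
- A reader might infer that the composite is necessarily biased upward. That needs both raw sums and an item set that changes within a person. The plan specifies neither.
- A reader might infer that requiring a CVD risk factor at entry builds a sizeable gain into even a fixed 5-item score. That would need selection on the baseline items themselves, whereas the plan selects at an earlier screening.

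**Conclusion.** The concern holds in this form: Aim 3 has no fixed clinical outcome, the one stated scoring rule lets record laboratory availability set a person's items, and the effect wording goes beyond a single-group design.

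The between-person difference in items follows directly from section 6. The remaining sizes are conditional. The 14-37% chance improvement rests on reading the outcome as the action-plan factor, on only the worst level being eligible, on r of 0.7-0.9 with 30-50% not at goal, and on the selection value being the baseline value. The 1.5-2.2 points per person rest on 0/1/2 scoring, raw sums and a change from 5 to 7 items within a person. These figures show how far the readings can diverge with no true change; they do not predict this study's result. The study remains worth doing, and the plan should be tightened before analysis.

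**What to change.** 1. In 14.1 (Specific Aim 3) and 12.1, make the inferential clinical outcome the within-person change in the 5-item score from baseline to one visit named in advance, for example the 3-month follow-up. Use the same five items and one stated scoring of the three levels for all participants at every visit. Count worsening, and estimate the change in the planned mixed model. Handle a missing item by the planned imputation, not by changing the item set.
2. Make the 7-item score supportive, in participants with both record items at both visits.
3. Report the action-plan factor descriptively (better, same, worse), with no test against zero.
4. In sections 1, 2 and 14.1 and in the conclusion, write *within-person change* instead of effect. For the CVD outcomes only, add *under HHMB delivered together with the provider strategies*.
5. At most, note that entry on a risk factor may leave some regression to the mean of unknown size.

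Cost: wording and pre-specification only, with no change to delivery and no added data collection. Lipids and glucose become supportive. The inferential score leans more on self-report, from participants coached on the same items. Blood pressure may be missing for some, so the imputation rule must be written out. The headline becomes less causal, and the later choice of outcome, visit and scoring is given up.
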